## **5.3    Characteristics of an Adverse Event**

### **5.3.1    *Relationship to Study Intervention***

To assess relationship of an event to study intervention, the following guidelines are used:

1. Related (Possible, Probable, Definite)
  - a. The event is known to occur with the study intervention.
  - b. There is a temporal relationship between the intervention and event onset.
  - c. The event abates when the intervention is discontinued.
  - d. The event reappears upon a re-challenge with the intervention.
2. Not Related (Unlikely, Not Related)
  - a. There is no temporal relationship between the intervention and event onset.
  - b. An alternate etiology has been established.

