**MRI Pain Attention Task:** The paradigm has 4 stimulus conditions presented in pseudo-random order. Individually determined, moderately painful (~47.5°C) stimuli will be delivered with a 9cm^2 thermode (Medoc) securely placed at the forearm. Subjects are instructed and trained before scanning as follows: (A: thinking) for the 'think'- condition: "think about pain stimulus and your chronic pain, its history and impact on your life, your expectation for your future life"; (B: sensing) for the 'feel'-condition: "feel the pain stimulus, be aware about how it makes you feel, its location, intensity and quality. "; (C: metacognition) for the 'reflect'-condition: "please notice whether you can observe how thoughts and emotions regarding your pain arise that may be familiar, whether they are really appropriate or not"; and (D: default) for the 'none'-condition: "do nothing specific, just wait for the stimulus to be over". The instructing cues: think, feel, reflect, and none, will be presented for 1s, followed by 20s of painful heat stimulation, followed by 39s baseline with neutral temperature to minimize habituation/ sensitization, until the start of the next trial. 7 trials of each condition will be performed for each subject. The task will be administered in four 7-min sequences.

This task has been used in prior studies without any risks for the participant.

A total of 50 participants will be enrolled into this study. 40 participants with cLBP will be enrolled into 4 consecutive MBPR classes ( $n = 10$  for each course) to iteratively refine the manualized MBPR protocol through mixed-methods evaluations after each round of MBPR. 10 participants with cLBP will be in the MBSR as the control group.

The first 30 participants enrolled in the study will be assigned to MBPR classes and the final 20 participants will be randomly assigned with ( $n = 10$ ) participants assigned to MBSR and ( $n = 10$ ) participants assigned to MBPR to test recruitment and randomization approaches.

**7.10 STANDARD CLINICAL PRACTICE: To what extent, if any, do the planned research procedures differ from the care that people would otherwise receive at this institution or the study site if not being done locally:**

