### **5.3.2    *Expectedness of SAEs***

The Study PIs and Independent Monitoring Committee will be responsible for determining whether an SAE is expected or unexpected. An adverse event will be considered unexpected if the nature, severity, or frequency of the event is not consistent with the risk information

previously described for the intervention.

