### **5.4.2 Adverse Event Reporting of Non-IND Studies**

SAEs that are unanticipated, serious, and possibly related to the study intervention will be reported to the Independent Safety Monitor(s), IRB, and NCCIH in accordance with requirements.

- Unexpected fatal or life-threatening AEs related to the intervention will be reported to the NCCIH Program Officer, and Independent Safety Monitor(s) within 3 days of the investigator becoming aware of the event. Other serious and unexpected AEs related to the intervention will be reported within 5 working days.
- Anticipated or unrelated SAEs will be handled in a less urgent manner but will be reported to the Independent Safety Monitor(s), IRB, and other oversight organizations in accordance with their requirements. and will be reported to NCCIH on an annual basis.
- All other AEs documented during the course of the trial will be reported to NCCIH on an annual basis by way of inclusion in the annual report and in the annual AE summary which will be provided to NCCIH and to the Independent Monitors. The Independent Safety Monitor(s) Report will state that all AEs have been reviewed.

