### **6.3 Stopping Rules**

This study will be stopped prior to its completion if: (1) the intervention is associated with adverse effects that call into question the safety of the intervention; (2) difficulty in study recruitment or retention will significantly impact the ability to evaluate the study endpoints; (3) any new information becomes available during the trial that necessitates stopping the trial; or (4) other situations occur that might warrant stopping the trial.

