### 7.4 Schedule and Content of Reports

The PI ([name]) will ensure continuous and close monitoring of participant safety and will report to the DSMB. Study progress and safety will be reviewed weekly by the PI and core study team. A report that will be submitted to the outside reviewer will be compiled annually and will include a list and summarization of adverse events. In addition, the report will address (1)

whether adverse event rates are consistent with pre-study assumptions; (2) reason for dropouts from the study; (3) whether all participants met entry criteria; and (4) whether continuation of the study is justified on the basis that additional data are needed to accomplish the stated aims of the study. If the DSMB requires an interim analyses based on the occurrence of severe adverse events, we will develop plans for conducting these in consultation with the statistician on this RCT.

The outside monitoring reports will be increased in frequency if two or more Serious Adverse Event's (SAE's) with attribution to study related procedures as possibly, probably or definitely related occur in a 6-month period of time. In this situation, SAE's will be reported monthly, and study procedures will be reviewed to determine if changes are needed to reduce the risk of SAEs.

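### The safety monitoring plan applies inconsistent standards of relatedness, so a serious injury from the fMRI or painful-heat task can carry two conflicting reporting clocks

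*Protocol*

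**What the plan says.** All DSMP sections below sit inside Protocol section 13.1.

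**Sections tied to the intervention**
- 5.3.1: "To assess relationship of an event to study intervention, the following guidelines are used". One way for an event to be classed Not Related is: "An alternate etiology has been established".
- 5.3.2: "An adverse event will be considered unexpected if the nature, severity, or frequency of the event is not consistent with the risk information", ending "previously described for the intervention".
- 5.4.2: unexpected fatal or life-threatening events related to the intervention go to NCCIH and the monitors in 3 days. For the rest: "Other serious and unexpected AEs related to the intervention will be reported within 5 working days". Anticipated or unrelated SAEs are handled less urgently and go to NCCIH once a year.
- 6.3, rule (1): the study stops if "the intervention is associated with adverse effects that call into question the safety of the intervention".

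**Sections that reach further**
- 5.1.2 defines an unanticipated problem by its relation to taking part in the research, including research procedures. Three criteria must all be met: unexpected, related or possibly related, and suggesting more risk than was known.
- 5.4.1 sends an unanticipated problem that is an SAE to the IRB, the monitors and NCCIH within 5 working days.
- 7.4 moves to monthly SAE reporting after two or more SAEs in 6 months "with attribution to study related procedures as possibly, probably or definitely related".

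**Table A (6.8)** has one row for SAEs that are unexpected and related (per occurrence to the monitors and NCCIH) and one for SAEs that are expected or unrelated (annual to both).

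**Risk descriptions.** DSMP 4.1 to 4.9 mention neither MRI nor heat. Protocol 12.1 describes MRI risks but its narrative does not mention the heat stimulus, and 12.2 refers back to 12.1. Protocol 7.9 defines the heat stimuli as moderately painful, yet says: "This task has been used in prior studies without any risks for the participant".

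**The concern.** The fMRI visits are the study's only in-person visits (Protocol 6.2), and the heat task is a research procedure that causes pain by design. The DSMP appears to have been written for the classes alone: its purpose statement describes only MBPR and MBSR. Whether it predates the imaging component is not stated.

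Attribution feeds the other safety rules. The reporting clock, the escalation count and stopping rule (1) all depend on what an event was judged to be related to. If the form asks only about the intervention, a harm caused by the scan has no box that says the study caused it. At stake are the speed with which the gravest events reach the monitors and whether the 7.4 count can be made reliably. Two staff members following different sections could also file the same event differently, each in good faith.

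**Working it through.** No power or event-rate calculation bears on this point. The check follows one event through each rule.

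**Exposure (Protocol 7.9 and 10.14)**
- 4 conditions × 7 trials = 28 stimuli per scan.
- Each trial lasts 1 + 20 + 39 = 60 s, so 28 trials take 28 min. This matches the four 7-minute sequences stated.
- Heat per scan: 28 × 20 s = 560 s. Two scans: 56 stimuli and 1,120 s, or 18.7 min, per fully scanned participant.

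This measures exposure only. It gives no probability of a serious event.

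**Step 1: is the event captured?** Yes. Recording starts at consent (DSMP 5.2).

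**Step 2: how does 5.3.1 class it?** In Protocol 10.14 the first scan is Visit 1, orientation is Visit 2 and the classes are Visits 3 to 10. A baseline-scan injury precedes any intervention, so it has no temporal relation to the intervention and it has another established cause. Both Not Related criteria apply. At the second scan (Visit 12) timing is arguable, but the other-cause criterion still applies.

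**Step 3: which clock follows?** The fast row of Table A needs unexpected *and* related. The slow row needs expected *or* unrelated. Unrelated alone is enough for the slow row, however unexpected the event is.

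**Step 4: compare the routes.**

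| Scan-caused event | 5.3.1 with 5.4.2 and Table A | 5.1.2 with 5.4.1, if all three criteria are met | If attribution also covered procedures |
|---|---|---|---|
| Unexpected, fatal or life-threatening | Annual | 5 working days | 3 days |
| Unexpected, other serious | Annual | 5 working days | 5 working days |
| Expected, serious | Annual | Not an unanticipated problem | Annual, but countable under 7.4 |

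In the first two rows the DSMP gives two clocks for one event. Where the unanticipated-problem route applies, only the first row changes: from 5 working days (7 calendar days, counting one weekend) to 3 days.

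**Step 5: the 7.4 count.** The trigger does not require unexpectedness. It needs possible, probable or definite attribution to study procedures. Section 5.3.1 uses those three grades, but only for the intervention, so the attribution that 7.4 counts is not recorded on that scale.

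**Step 6: expectedness.** Under 5.3.2 read literally, a scan event of a kind described in 12.1 is unexpected, because it is not among the risks of the intervention. Under 5.1.2 it is expected, because the protocol-related documents describe it. The two sections give opposite answers.

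**The case against.** The strongest reply is that the DSMP already covers research procedures where it matters most. An adverse event is defined by participation in the study (5.1.1), and 5.1.2 and 7.4 both reach procedures. The omission of scan and heat risks also works toward faster reporting: a serious heat injury would be unexpected, caused by a research procedure and suggestive of more risk than was known. It would then meet all three criteria and be due in 5 working days. This stands, and it is why the finding is a conflict between sections and not an absence of cover.

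Three stronger readings are tempting, and the documents do not support them.
- *That relatedness is judged against the intervention alone throughout the plan.* Sections 5.1.2 and 7.4 show otherwise.
- *That a scan injury would stay out of the monitors' sight for up to a year.* This rests on one Table A row. Section 6.5 gives the monitors progress reports including AEs semi-annually. Section 5.3.2 makes the monitoring committee jointly responsible for judging SAE expectedness. Section 5.4.2 also reports unrelated SAEs to the monitors and the IRB under those bodies' own requirements.
- *That the stopping rules would miss such events.* Only rule (1) of 6.3 is limited to the intervention; rules (3) and (4) are general. The halting rule in 5.5 speaks of related events without saying related to what, so it is ambiguous but does not exclude procedures.

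It can also be said that 7.4 states its own standard and that nothing forbids a site from recording it. That is true, but a count that triggers escalation should not depend on an attribution that the plan's only scale does not ask for.

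Some evidence cannot be seen. Section 5.4 defers to IRB rules outside the documents, the consent pages were removed, and the tick-box states in 12.1 were lost. Heat discomfort may be disclosed there.

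**Conclusion.** The concern holds as an inconsistency within the DSMP. The sections that classify and report adverse events use a narrower standard than those on unanticipated problems and escalation, and one serious scan injury can draw two different clocks. Two gaps are clear: the 3-day rule leaves out fatal or life-threatening events caused by a procedure, and the 7.4 trigger relies on an attribution that 5.3.1 does not record. The risk lists do not match either: the MRI risks of 12.1 are missing from DSMP section 4, heat is in neither narrative, and the no-risk sentence in 7.9 sits beside stimuli defined as painful.

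The size is modest. Where the unanticipated-problem criteria are met, one clock changes. The documents give no expected number of such events, so none is estimated here. The conclusion assumes that the intervention in 5.3.1 means MBPR or MBSR and not the scans. The DSMP does not define the term, but its purpose statement and risk list point that way. The passages should be reconciled before the plan is relied on.

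**What to change.** 1. In 5.3.1, record two attributions for every event: one to the intervention (classes and home practice) and one to study procedures (MRI, heat stimulation, questionnaires).
2. In 5.3.2, 5.4.2, Table A and 6.3(1), refer to the intervention or a study procedure, so that they agree with 5.1.2 and 7.4. State in 5.5 what a related event is related to.
3. Add MRI and heat stimulation to DSMP section 4, and heat stimulation to the narrative in Protocol 12.1.
4. Reconcile the no-risk sentence in Protocol 7.9 with the description of the stimuli in the same section.

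The cost is wording changes in the DSMP and application, one extra field on the adverse-event form, and a few more events counted as related. The time limits and the numerical trigger in 7.4 stay as they are.

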### **5.3.2    *Expectedness of SAEs***

The Study PIs and Independent Monitoring Committee will be responsible for determining whether an SAE is expected or unexpected. An adverse event will be considered unexpected if the nature, severity, or frequency of the event is not consistent with the risk information

previously described for the intervention.

### **5.3.3 Severity of Event**

The following scale will be used to grade adverse events:

1. Mild: no intervention required; no impact on activities of daily living (ADL)
2. Moderate: minimal, local, or non-invasive intervention indicated; moderate impact on ADL
3. Severe: significant symptoms requiring invasive intervention; subject seeks medical attention, needs major assistance with ADL

## **5.4 Reporting Procedures**

Serious Adverse Event reporting will be in accordance with the UCSF- Committee on Human Research Regulations and Code of Federal Regulation Title 21 Volume 5 Part 312.32.

We will also follow the UCSF IRB website for guidance in reporting serious adverse events  
<https://irb.ucsf.edu/adverse-event>.

### **5.4.1 Unanticipated Problem Reporting**

Incidents or events that meet the OHRP criteria for unanticipated problems require the creation and completion of an unanticipated problem report form. OHRP recommends that investigators include the following information when reporting an adverse event, or any other incident, experience, or outcome as an unanticipated problem to the IRB:

- Appropriate identifying information for the research protocol, such as the title, investigator's name, and the IRB project number;
- A detailed description of the adverse event, incident, experience, or outcome;
- An explanation of the basis for determining that the adverse event, incident, experience, or outcome represents an unanticipated problem;
- A description of any changes to the protocol or other corrective actions that have been taken or are proposed in response to the unanticipated problem.

To satisfy the requirement for prompt reporting, unanticipated problems will be reported using the following timeline:

- Unanticipated problems that are serious adverse events will be reported to the IRB, Independent Safety Monitor(s), and NCCIH within 5 working days of the investigator becoming aware of the event.
- Any other unanticipated problem will be reported to the IRB, Independent Safety Monitor(s), and NCCIH within 10 working days of the investigator becoming aware of the problem.

All unanticipated problems should be reported to appropriate institutional officials (as required by an institution's written reporting procedures), the supporting agency head (or designee), and OHRP within one month of the IRB's receipt of the report of the problem from the investigator.

### **5.4.2 Adverse Event Reporting of Non-IND Studies**

SAEs that are unanticipated, serious, and possibly related to the study intervention will be reported to the Independent Safety Monitor(s), IRB, and NCCIH in accordance with requirements.

- Unexpected fatal or life-threatening AEs related to the intervention will be reported to the NCCIH Program Officer, and Independent Safety Monitor(s) within 3 days of the investigator becoming aware of the event. Other serious and unexpected AEs related to the intervention will be reported within 5 working days.
- Anticipated or unrelated SAEs will be handled in a less urgent manner but will be reported to the Independent Safety Monitor(s), IRB, and other oversight organizations in accordance with their requirements. and will be reported to NCCIH on an annual basis.
- All other AEs documented during the course of the trial will be reported to NCCIH on an annual basis by way of inclusion in the annual report and in the annual AE summary which will be provided to NCCIH and to the Independent Monitors. The Independent Safety Monitor(s) Report will state that all AEs have been reviewed.

## 5.5 HALTING RULES

Review of any serious, unexpected, and related AEs by the Medical Monitor, DSMB/ Independent Safety Monitors, IRB, the sponsor, or relevant local regulatory authorities may result in suspension of further study interventions/administration of study product at a site. The study sponsor retains the authority to suspend additional enrollment and study interventions/administration of study product for the entire study, as applicable.

## 6 QUALITY CONTROL AND QUALITY ASSURANCE

We will develop standard operating procedures (SOPs) that will describe:

- Staff training methods and how such training will be tracked: All key study personnel and those involved in obtaining consent will maintain updated CITI human subjects training. This will be tracked and reviewed by the Project Director yearly or more frequently, with submission of each IRB modification or renewal (i.e. at least yearly).
- How data will be evaluated for compliance with the protocol and for accuracy in relation to source documents.
- The documents to be reviewed (e.g., CRFs, attendance lists, questionnaires, audio or video recordings), who is responsible, and the frequency for reviews.
- Who will be responsible for addressing quality assurance issues (correcting procedures that are not in compliance with protocol) and quality control issues (correcting errors in data entry). It is anticipated that QA review and data verification will be performed by someone other than the individual originally collecting the data, or by double-data entry. The frequency of internal QA review and measures to be taken for corrective action, e.g., for trends in errors, should be included. A statement reflecting the results of the ongoing data review will be incorporated into the Annual Report for the Independent Safety Monitor(s).

### 6.1 Subject Accrual and Compliance

#### 6.1.1 *Measurement and Reporting of Subject Accrual*

Review of the rate of subject accrual and compliance with inclusion/exclusion criteria will occur monthly during the recruitment phase to ensure that a sufficient number of participants are being enrolled, in keeping with proposed recruitment projections, and that they meet eligibility criteria and fulfill the targeted ethnic diversity goals outlined in the grant proposal (Targeted/Planned Enrollment Table).

#### 6.1.2 *Measurement and Reporting of Participant Adherence to Treatment Protocol*

Data on adherence to the treatment protocol will be collected weekly by research staff and reviewed monthly by the PI ([name]). Adherence of participants will be evaluated by attendance list. Available data on adherence to all three indices using an earlier version of the study intervention suggests that 20% or fewer participants had poor adherence. If adherence falls below the suggested rate, which might inhibit the ability of the study to test its primary hypotheses, the PI will suggest a conference call for study investigators to discuss methods for improving adherence.

### 6.2 Justification of Sample Size

The primary goal of this study is to prepare for a rigorous RCT comparing efficacy of the MBPR intervention to alternatives. We are not aiming to test efficacy in the current study and do not have adequate sample size for this assessment. The proposed sample sizes were selected based on the numbers we estimate will be needed to adequately refine the intervention and assess its acceptability and feasibility, and to obtain variance estimates to inform future work. However, we will conduct **exploratory analyses** to obtain estimates of ICCs of the repeated measures from linear mixed models, and preliminary estimates looking at Pearson correlations between changes in pain outcomes and changes in psychometric scale measures that we understand to be potential mediators of change in pain intensity following mindfulness interventions, e.g. PCS-SF, FABQ-PA, and MAIA-2. Although using all participants across all iterations of MBPR is limited by variations in

the intervention, with an exploratory total MBPR sample size of 40, we will have 80% power (two-tailed alpha = 0.05) to detect a statistically significant correlation if the expected Pearson correlation coefficient comparing change scores for pain outcomes with change scores for psychometric scale measures is 0.43 or greater. If we experience a loss to follow-up rate of 10% in our classes, the sample size per subsequent class will be increased to 11 subjects.

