## 9.0 Sample Size and Eligibility Criteria

### 9.1 ENROLLMENT TARGET: How many people will you enroll:

If there are multiple participant groups, indicate how many people will be in each group:

A total of 50 participants will be enrolled into this study. 40 participants with cLBP will be enrolled into 4 consecutive MBPR classes ( $n = 10$  for each course). 10 participants with cLBP will be in the MBSR as the control group.

Specifically, the first 30 participants of the total 50 enrolled in the study will be assigned to MBPR classes and the final 20 participants will be randomly assigned to MBSR ( $n = 10$ ) or to MBPR ( $n = 10$ ) to test recruitment and randomization approaches.

**9.3 SAMPLE SIZE JUSTIFICATION: Explain how and why the number of people was chosen. For multi-site studies, this is referring to the number that will be enrolled across all sites:**

The primary goal of this study is to prepare for a rigorous RCT comparing efficacy of the MBPR intervention to alternatives. We are not aiming to test efficacy in the current study and do not have adequate sample size for this assessment. The proposed sample sizes were selected based on the numbers we estimate will be needed to adequately refine the intervention and assess its acceptability and feasibility, and to obtain variance estimates to inform future work. However, we will conduct **exploratory analyses** to obtain estimates of ICCs of the repeated measures from linear mixed models, and run linear mixed models with pain as outcome, and an interaction between study period and psychological variables (e.g. PCS-SF, FABQ-PA, and MAIA-2) as predictors, with nested random effects of person nested within class group. Although using all participants across all iterations of MBPR is limited by variations in the intervention, with a total MBPR sample size of 40 (out of 50 total enrolled, with a control/MBSR group of  $n = 10$ ), we will have 80% power (two-tailed alpha = 0.05) to detect a statistically significant correlation if the expected coefficient of determination is 0.43 or greater.

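### The 80% power figure counts all 40 enrolled MBPR participants as complete pairs, and the 11-per-class top-up is not reconciled with a total enrolment of 50

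*Protocol*

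**What the plan says.** DSMP 6.2 (Justification of Sample Size) says that, "with an exploratory total MBPR sample size of 40, we will have 80% power" at a two-sided 5% level. The effect is a Pearson correlation "comparing change scores for pain outcomes with change scores for psychometric scale measures is 0.43 or greater". The paragraph then gives a conditional rule: if loss to follow-up reaches 10% in the classes, "the sample size per subsequent class will be increased to 11 subjects".

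Protocol 9.1 sets enrolment: "A total of 50 participants will be enrolled into this study", of whom "40 participants with cLBP will be enrolled into 4 consecutive MBPR classes" of 10 each, with 10 more in MBSR. The first 30 go to MBPR and the last 20 are randomised 10 and 10. Protocol 7.9 and 10.9 repeat the total of 50 and the 30/20 split. DSMP section 1 (Purpose of Study) also gives 50, made up of 40 MBPR and 10 MBSR. None of these places mentions the top-up or a maximum above 50.

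Protocol 9.3 carries a similar power sentence without the top-up rule, and words the effect differently: "if the expected coefficient of determination is 0.43 or greater".

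On retention, Protocol 7.13 and the SAP cite 97% outcome completion at 12 weeks in another mindfulness study. The SAP allows multiple imputation if indicated; Protocol 7.13 allows mixed models if indicated.

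**The concern.** A correlation between two change scores uses only people with pre and post values on both scales. DSMP 6.2 puts the enrolled number, 40, where the number of complete pairs belongs, although the same paragraph foresees that people may be lost. The top-up applies only to later classes, so losses in the class that triggers it are not replaced.

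The top-up also changes the sample size. Once used, it takes enrolment past the 50 stated elsewhere, including in the same DSMP, and no text says which statement governs. The trigger is not remote: in a class of 10, one lost participant is 10%. At stake are a slightly optimistic power statement for an exploratory analysis, and an enrolment number that staff, the IRB and the funder could read in two ways part-way through the study.

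**Working it through.** **Inputs.** r = 0.43, two-sided alpha 0.05, n = 40 (DSMP 6.2); four MBPR classes of 10 and one MBSR group of 10 (Protocol 9.1); 10% loss as trigger and 11 per later class (DSMP 6.2); 97% retention (Protocol 7.13, SAP).

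**Formula (Fisher z).** Power = Phi(atanh(r) × sqrt(n − 3) − 1.96), with atanh(0.43) = 0.460. The correlation detectable with 80% power is tanh((1.96 + 0.842)/sqrt(n − 3)). An exact bivariate-normal calculation serves as a check; it runs about one point higher.

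**1. Reproduce the stated figure.** At n = 40: 0.460 × sqrt(37) − 1.96 = 0.838, so power is 79.9% (80.9% exact). The stated 80% is right for 40 complete pairs. There is no reserve: at n = 39 the exact power is already 79.9% (78.8% by Fisher z).

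**2. Power on evaluable pairs.**

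| Scenario | MBPR enrolled | Pairs | Power at r = 0.43 (Fisher z) | Detectable r at 80% (Fisher z) |
|---|---|---|---|---|
| No loss | 40 | 40 | 79.9% | 0.43 |
| 3% loss (cited 97% retention) | 40 | 40 × 0.97 = 38.8 | 78.6% | 0.44 |
| 10% loss, top-up not used | 40 | 40 × 0.90 = 36 | 75.2% (76.4% exact) | 0.45 |
| 10% loss, classes 2 to 4 raised to 11 | 10 + 11 + 11 + 11 = 43 | 43 × 0.90 = 38.7 | 78.5% | 0.44 |

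Even with the top-up at its fullest, the expected number of pairs stays just under 40. Keeping 40 pairs after 10% loss would need 40/0.90 = 44.4, so 45 MBPR participants.

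**3. Enrolment under the rule.** Raising one, two or three later MBPR classes gives 41, 42 or 43 MBPR participants. With MBSR kept at 10 the total is 51, 52 or 53. If all three are raised and the MBSR group also goes to 11, it is 54. DSMP 6.2 does not say whether the rule covers the MBSR group. Every use of the rule exceeds 50.

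**4. How likely is the trigger?** If losses are independent (an assumption) and the trigger is read on the first class alone, the chance of at least one loss among 10 is 1 − 0.97^10 = 26% at 3% loss, and 1 − 0.90^10 = 65% at 10% loss.

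**The case against.** The strongest reply has four parts.

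- *Ten percent is a trigger, not a planning assumption.* This stands. A reader might infer that the plan expects 10% loss and therefore really has 75% power. The documents do not say so: the 10% is introduced with an if, and the only retention figure cited is 97%, at which the shortfall is about one point.
- *Fifty is a target, and a conditional top-up is not a contradiction.* This stands in part. Section 9.1 is headed as an enrolment target, and the conflict appears only if the rule is used. But 50 is stated flatly in four places, one of them in the same DSMP, with no maximum. A reader might also infer that holding 50 as a ceiling would shrink the randomised cohort to 18 (50 − 10 − 11 − 11). No passage describes such a cohort or calls 50 a ceiling.
- *The analysis described elsewhere does not need complete pairs.* Protocol 9.3 describes linear mixed models, and the SAP (Hypothesis 6) regression with imputation if indicated. These may use partial records, but they do not supply the missing pairs in the Pearson calculation behind the DSMP 6.2 figure.
- *Nothing turns on it.* Largely right. Protocol 9.3 and DSMP 6.2 say the size was chosen for refinement, feasibility and variance estimates. The correlation is exploratory, and the SAP expects no statistical significance.

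**Conclusion.** The point holds as a minor correction. DSMP 6.2 states 80% power on enrolled rather than evaluable participants. The overstatement is about 1 point at the cited 97% retention, about 1 to 2 points at 10% loss with the full top-up, and about 4 to 5 points at 10% loss without it. Separately, the 11-per-class rule implies a total of 51 to 54, which no section reconciles with 50.

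This rests on reading 0.43 as a Pearson correlation, as DSMP 6.2 does, on a complete-pairs analysis, and on the same loss rate in every class. The wording in Protocol 9.3 is a separate discrepancy: a coefficient of determination of 0.43 means r = sqrt(0.43) = 0.656, for which 40 pairs give 99.8% power and about 16 would suffice. The stated 80% fits only r = 0.43.

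A reader might take this for an arithmetic error or a threat to the study's purpose. It is neither: the 80% is correct for 40 pairs, and the main aim is feasibility.

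**What to change.** 1. In DSMP 6.2, and in Protocol 9.3 if the figure is kept there, state power on evaluable pairs, one scenario at a time: 80% power at r = 0.44 with about 39 pairs, or at r = 0.45 with 36. Do not merge the scenarios into one range. At 10% loss, about 39 pairs applies only if the top-up is used and 36 only if it is not. Settle in the same edit whether 0.43 is a correlation or a coefficient of determination.
2. Make Protocol 9.1 (with 7.9, 10.9 and DSMP 1) agree with DSMP 6.2. Either give 50 as the target with a maximum of 54 under the rule, saying whether the MBSR group is included (the maximum is 53 if not), or drop the rule and quote the 36-pair figure for 10% loss.

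The cost is wording and a slightly less favourable power statement for an exploratory analysis. Keeping the rule adds up to 4 participants to the 50, but none beyond what the rule already implies. DSMP 2 requires amendments other than minor administrative ones to go to the funder before IRB approval is sought, so this is easier to settle before a class triggers the rule.
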